Key Protocol Contributors	[name], MBChB, MRCS
	Email: [contact]
	[contact] [name]

5 Study Summary

Full Study Title	Evaluation of the GRI gentleheel® incision device for adult fingertip blood sampling - intended use extension
Internal ref. no. (or short title)	Evaluation of the GRI gentleheel® incision device for adult blood sampling.
Study Design	Prospective, interventional, non-randomised, single-centre study.
Study setting	Single site
Planned Size of Sample	50
duration	5 days
Planned Study Period	4 weeks for the purpose of recruitment
Research Question/Aim(s)	Can GRI gentleheel® incision device be safely used by lay members of the adult population for the purpose of capillary blood sampling from the fingertip.

6 Funding and Support

FUNDER	FINANCIAL AND NON FINANCIAL SUPPORT GIVEN
Mowgli Innovation	Financial support
Mowgli Innovation	Non-financial support (Sponsor)

ROLE OF STUDY SPONSOR AND FUNDER

The role of the study funder is to provide financial support to the study. The sponsor takes on ultimate responsibility for the initiation and management the research, providing the facilities in which the study patients will take part in the trial. The sponsor will ensure primary responsibility for ensuring that the design of the study meets appropriate standards and that arrangements are in place to ensure appropriate conduct and reporting.

ROLES AND RESPONSIBILITIES OF STUDY MANAGEMENT COMMITEES/GROUPS & INDIVIDUALS

The Principle Investigator and the study co-ordinator will be responsible for patient recruitment, and randomisation, data collection and analysis, annual progress report as well as final report preparation. Patient & Public Involvement Groups will not be involved in the design and implementation of the study.

7 Protocol Contributors

IRAS Number: 311621

The study sponsor (Mowgli Innovation) will be involved in the review of the study protocol, data analysis and interpretation as well as manuscript writing and dissemination of the results. The key protocol contributors, the principal investigator and the study co-ordinator will assist the study sponsor in these tasks, however, the final decision regarding the study design, conduct of the study, data collection and analysis, annual progress report and final report preparation lies with the principle investigator.

Key Protocol Contributor	[name], MBChB, MRCS	
	Email: [contact]	
	[contact] [name]	

8 Contents

1	Title	Page	2	2
2	Rese	earch	Reference Numbers	2
3	Sign	ature	Page	3

12.1 Background – Current Solutions (Principles and Disadvantages)

One of the most commonly performed procedures in the health sector is venepuncture, with millions carried out every year in the United Kingdom. Until recently, venepucture has been the mainstay of obtaining intravenous access for the purpose of blood sampling. This involves using a needle to puncture a peripheral vein in order to access the venous circulation in order to draw blood, which is then sent to the lab for analysis. However, venepuncture is not without potential complications, which include patient discomfort, echhymosis, risk of sharp injury to the phlebotomists, and anemia associated with repeat venepuncture (1-3). Furthermore, in patients with inadequate or damaged veins (such as burns patients), those with arms in casts, and in cases of obesity, venepuncture can be challenging, often requiring multiple attempts to obtain an adequate blood sample. Repeated large-volume sampling is undesirable for patients, especially for patients with chronic disease who require regular sampling or when maintaining blood volume is critical (4,5). In such instances, capillary blood testing can be performed (6). This involves using a micro lancet to make a small, 1-2mm incision in the fingertip resulting in pin-point bleeding. This blood is collected into blood collection tubes and sent for analysis. The use of micro lancets to extract blood for analysis is not new. Diabetics have been using this for decades to obtain real-time blood sugar measurements (7), and their use is commonplace in neonates, using the heal to extract blood samples.

With the advent of point-of-care testing (POCT) in a variety of locations such as GP surgeries, the community and in the Emergency Department, the concept of capillary blood testing is becoming increasingly more relevant (4,8). POCT is any diagnostic testing performed onsite, with the results leading to potential change in patient care. Capillary blood samples are now routinely used for checking a variety of blood parameters such as glucose, glycosylated haemoglobin, cholesterol, haemoglobin, bilirubin and electrolytes (4,8,9). Capillary blood sampling has also been used for rapid screening for HIV, hepatitis B & C and for drug monitoring (10,11).

Capillary blood sampling has clear advantages over traditional venepucture: it is less invasive, less painful, requires fewer consumables, is less resource intensive with regards to the need for a phlebotomist, clinical space, storage and logistical requirements (4,12). Furthermore, venipuncture requires substantial training to perform the collection, and success in obtaining a sample is dependent on the skill of the phlebotomist performing the blood draw in addition to the accessibility of the patient's veins. The use of a hypodermic needle for venipuncture not only poses the risk of needle-stick injury to the phlebotomist but can also cause pain and anxiety for the patient, which can be a barrier to receiving proper healthcare. Therefore, there is a real need for a reliable and easy way to obtain blood for use in capillary blood sampling to meet the growing need in this area of healthcare provision.

12.2 Challenges with Capillary Blood Collection

IRAS Number: 311621

Traditional methods of capillary blood sampling work by using a micro lancet to puncture the skin. A small plastic device comes pre-loaded with a sterile lancet. The device is held against the side of the fingertip and is either pushed into the finger to activate (for contact-activated lancets) or a button is pressed on the device, deploying the spring-loaded lancet at high speed, piercing the capillaries located in the dermis and resulting in bleeding. The finger is squeezed to expedite the flow of blood, which is collected and used for analysis.

One potential disadvantage of capillary blood sampling is difficulty in reliably obtaining a blood sample of sufficient volume and quality for testing. The practice of lancing 'alternate sites' such as the arm, thigh, or palm has been used to alleviate the pain associated with fingertip sampling, but the lower capillary densities of these regions make it even more

difficult to obtain an adequate sample volume for testing (13).

A recent review article tested several lancet-based finger capillary blood sampling devices available on the market on adult volunteers. It found the mean volume of blood extracted varied from 37.3 μ L to 265.0 μ L, depending on the design of the lancet (needle versus blade), with all needle-based devices yielding a volume below 100 μ L (8).

Typical routine blood tests require two separate blood bottles (one for conducting haematological tests such as haemoglobin levels, and another for biochemical profile, renal and liver function tests). The volume of blood required to analyse these samples varies according to the lab, and typically this ranges from 100 μ L to 500 μ L. With the current lancet-based systems, it is not uncommon to require the puncture of several fingers to obtain sufficient volume, resulting in increased pain to the patient.

Hemolysis (breakdown of red blood cells), lipaemia (contamination of the sample with microfat particles) and sample dilution with extracellular fluid are recognized complications of capillary blood sampling (6,14), which are often due to repetitive squeezing of the finger at the puncture site in order to extract sufficient blood from the finger.

Therefore, there is a real need for a lancet-based device that is not only safe and easy to use but more importantly one that can provide sufficient blood volume.

12.3 Proposed Solution

IRAS Number: 311621

Our solution to the problem is to modify the use of a pre-existing device on the market (gentleheel®) to address the shortcomings of blood capillary sampling devices with regards to obtaining an adequate volume of blood. The gentleheel® device, is a heel incision device designed for use in new-born blood sampling. This device is CE-marked and FDA approved. It offers a safe and efficient way of acquiring blood samples from the heels of new-borns and toddlers. The device is engineered with the following features to ensure ease of use and minimal discomfort for the patient:

- Ergonomic design for improved handling.
- Multiple visual indicators reinforce incision site.
- Incision devices are less traumatic than punctures.
- Tri-bevel blade generates a smoother, less traumatic incision.
- Hardened stainless steel blade improves incision accuracy.
- Permanent blade retraction minimizes possible reuse or injury.
- Welded plastic casing prevents accidental exposure to the blade.

The fundamental difference between gentleheel® and other devices is the greater volume of blood that can be extracted from a single finger prick. This is due to the type of lancet and the way it is deployed. In contrast to traditional devices that use a needle as a lancet that punctures the skin, gentleheel ® utilises a blade, creating a 3.0 mm area of dermal bleeding, resulting in improved blood flow, allowing for increased volume of blood to be collected with the potential to reduce the aforementioned limitations with needle-based lancets. The incision depth is 2.0 mm, in accordance with safety limits recommended by the World Health Organization (WHO) guidelines on the use of capillary blood sampling devices (6).

This device, however, is only licensed for use by healthcare professionals on the heels of new-borns and toddlers. The intention of this study is to extend the utility of this device by investigating its use in capillary blood sampling from adult fingertips.

12.4 Investigational Device

IRAS Number: 311621

This section shows gentleheel® device and contains a schematic of the mechanism of action.

Figure 1: Picture of the gentleheel® device model Toddler.

[figure not shown]

Figure 2: Schematic drawings showing from left to right the removal of the trigger lock.

[figure not shown]

Figure 3: Schematic drawings showing from left to right the sweeping motion of the tri-bevel stainless steel blade after the blade is deployed.

13 Research Question/Aims

Can gentleheel® incision device be used by lay members of the public without intervention from medically qualified practitioners for the purpose of capillary blood sampling in the fingertip?

14 Study Objectives

This clinical investigation is designed to collect information related to the performance and safety of this device during blood sampling in adult fingertips.

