14.1 Primary Objectives

- 1. To determine if a volume of 500 microlitres to 1.1 millilitre of blood can be collected after a single lancing of the fingertip with gentleheel®.
- 2. To assess pain from fingertip lancing with gentleheel®.

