15.3 Investigation Design

IRAS Number: 311621

A sample size of 50 patients will be used. Each patient will perform two separate incisions on the middle and ring fingers, resulting in 100 blood draws. During the procedure, the following data will be documented:

- the location of the incisions (which finger middle/ring and which side of the fingertip ulnar/radial).
- the volume of blood obtained from each incision;
- the pain level experienced for each incision;

After appropriate explanation of the procedure to the patient, he/she will sign the Informed Consent Form to confirm that their participation in the study is voluntary. All required data as per the CRF will be obtained and the patient will then collect blood from 2 incisions on his/her fingertips.

All collected blood samples will be used for volume measurement and discharged afterwards. Following the blood collection from all 2 incisions, the patient will be appropriately monitored, until he/she leaves the investigational site. Any adverse event if presented will be documented before the patient leaves the investigational site.

Please see Table 1 for an overview of the data being collected for each subject on the day of the blood collection procedure.

Table 1: Overview of the data to be collected for each subject in the day of the blood collection procedure.

Incision #	Finger identification (middle/ring)	Incision position (radial/ulnar)	Volume of blood collected (µI)	Pain level (0 to 10)
1				
2				

Within 5 days of procedure, a follow-up telephone call will take place in order to assess if any adverse events occurred.

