16.3 Analysis Method

IRAS Number: 311621

All data will be anonymised prior to analysis.

The statistical analysis will be done on the ITT population. In case more than 10% of patients present major violations to the protocol (defined as any deviation which may significantly impact the evaluation of the endpoints), primary endpoints analysis will be re-assessed and documented appropriately.

Descriptive statistical data will be used to summarize the characteristics of subjects at the time of inclusion (demographics, baseline and procedure data).

The primary and secondary objectives will be presented as a proportion with 90% confidence intervals (CIs). For other objectives, quantitative variables will be summarized by the number of patients (n), mean, standard deviation (SD) and range; qualitative variables will be summarized by frequency and percentage of patients; rates will be summarized by the numerator, denominator, rate, and its 90% CI. Descriptive statistics only will be provided for AE data.

A complete adverse event description will be done: total number of events and number of patients with at least one of the respective categories AEs, ADEs, SAEs, SADEs, USADEs. Investigation Assessments

17 Participating Investigator and Site

One investigational site in the United Kingdom will be chosen for this study. This will take place at King's College London, in a dedicated research facility which routinely carries out blood sampling related studies.

The Principal Investigator is experienced in the field of phlebotomy and capillary blood sampling and collection. All training on how to use the gentleheel® device will be provided to the Investigator by the Sponsor of the study. A Study Coordinator will be available to ensure the data is collected, and any immediate adverse events noted.

18 Investigation Handling Procedures

The investigational device will be provided to the site by the sponsor. Each device will be entered and tracked on the Device Accountability Log. Once an investigational device is used, it should be discarded per the investigational site's disposal procedure. All devices are one-time use only. The devices should be kept in a secure location, in a cool, dry place.

19 Anticipated Adverse Events

Adverse events that may possibly be caused by, or associated with, the use of the gentleheel® for capillary blood sampling in adult fingertips include:

- Fainting during the incision procedure.
- Pain during and after the incision procedure.

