- Bruising.

IRAS Number: 311621

- Hematoma.
- Excessive bleeding requiring more than 5 minutes of compression to stop.
- Infection at the incision site.

20 Anticipated Benefits to the Patients

The anticipated benefits of the gentleheel® for capillary blood sampling in adult fingertips is to improve the user / patient experience of capillary blood collection:

- Ensure collection of an adequate volume of blood from a single finger puncture.
- Minimal discomfort from the procedure blade-based incision devices are less traumatic than needle-based puncture devices (15). The sweeping motion of the tribevel stainless steel blade of the gentleheel® device allows for a smoother and less traumatic incision.
- The gentleheel®'s ergonomic design is easy to use and user friendly.

21 Minimization of Risks

IRAS Number: 311621

This investigation will be monitored to ensure the identification, documentation and analysis of all adverse events, compliance with the Clinical Investigation Plan, the terms of the participating study approval committee to protect the safety and rights of all patients, and applicable local regulations. In addition, risks have been minimized through selection of the Investigator who is experienced in capillary blood sampling.

Although all risks associated with the intended procedure and device may not be fully known at this time, the risks have been identified through an exhaustive literature search and represent the most up-to-date understanding of risks associated with the proposed procedure. The sponsor will employ the following measures throughout the course of this investigation to minimize these risks.

- The Sponsor has clearly defined inclusion and exclusion criteria and will monitor adherence to them, to ensure that only appropriate patients are enrolled.
- The Investigator will obtain informed consent.
- The Sponsor will select the investigational site that has a sufficient level of expertise needed to support and to manage adverse events that could arise and to provide appropriate alternative measures if needed.
- The Investigator will ensure that the follow-up of the patients are consistent with current medical practices and provide the institutional standard of care in line with expert medical judgment.
- The Investigator will report all Safety Adverse Events (SAE).

22 Follow-up of Adverse Events and Adverse Device Effects

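### The aim is lay use without medical intervention, but no objective or listed data item records help during an incision, so that element cannot be shown

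*Protocol*

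**What the plan says.** The Protocol states its question twice. Section 13 asks "Can gentleheel® incision device be used by lay members of the public without intervention from medically qualified practitioners" for fingertip sampling. The Study Summary (Section 5) asks "Can GRI gentleheel® incision device be safely used by lay members of the adult population". Section 12.3 explains why the user matters: the current licence covers healthcare professionals sampling young children's heels. The extension therefore changes the operator as well as the body site.

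The objectives are narrower. Section 14.1 lists "To determine if a volume of 500 microlitres to 1.1 millilitre of blood can be collected after a single lancing of the fingertip" and "To assess pain from fingertip lancing with gentleheel". Section 14.2 lists adverse event reporting only, and the synopsis (Section 23) repeats the same three items.

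Sections 15.3, 15.5 and 15.6 make the patient the operator, with written instructions and a prior explanation. Table 1, titled "Overview of the data to be collected for each subject in the day of the blood collection procedure", has columns for finger, side, volume and pain. The timeline table (Section 15.4) adds consent and adverse events. The flow chart adds demographics, medical history and concomitant medication. Section 22.1 has device deficiencies recorded on the CRF.

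On staff, Section 17 says "A Study Coordinator will be available to ensure the data is collected, and any immediate adverse events noted", alongside an investigator experienced in capillary sampling. No section says what help staff may give while the patient makes the incision or collects the blood.

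**The concern.** What distinguishes the Section 13 question from a plain performance study is the absence of professional intervention, and none of the planned measurements captures it. Sampling takes place in a research facility with trained staff on hand. A patient who is told to reposition the device, reminded to remove the trigger lock or helped to fill the tube contributes the same volume and pain entries as one who managed alone. A user's failed first activation has no listed field either; the device-deficiency record concerns faults of the device, not of its use.

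At stake is the claim made afterwards. Good volume and pain results could be read as support for unsupervised lay use although nobody recorded how much supervision was needed. Help not noted on the day cannot reliably be reconstructed later.

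**Working it through.** No figure in the Protocol is in dispute. Its count reproduces: 50 subjects × 2 incisions = 100 draws (Section 16.1). The choice of 50 cannot be re-derived, because no target interval width or expected proportion is given. The check therefore has three parts.

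**1. Question against data.**

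| Element of the aim | Where it is measured |
|---|---|
| Operator is a lay adult | By design: the patient makes the incision (15.3, 15.6) |
| Adequate sample | Volume per incision (14.1, Table 1) |
| Safety | Adverse events on the day and at the call (14.2, 15.4, 15.7) |
| Tolerability | Pain 0–10 per incision (14.1, Table 1) |
| No intervention by medically qualified staff | No objective, no listed item |
| User activates the device at first attempt | No objective, no listed item |

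**2. What unrecorded help could hide (assumed figures).** Suppose 90 of 100 incisions reach the volume and h were helped. The number both unaided and adequate lies between 90 − h (every helped incision was adequate) and the smaller of 90 and 100 − h (as many helped incisions as possible were inadequate).

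- h = 10: from 80 to 90.
- h = 20: from 70 to 80.

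If the question is instead how many would have been adequate had no help been given, and help never made matters worse, the upper limit is 90 in both cases: 80 to 90 for h = 10, and 70 to 90 for h = 20. The listed data look the same whatever h is.

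**3. Whether 50 subjects can support the missing measure.** Section 16.3 uses 90% intervals. For x of n subjects, the exact (Clopper-Pearson) limits are:

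- lower = the 5% quantile of Beta(x, n − x + 1);
- upper = the 95% quantile of Beta(x + 1, n − x), or 1 if x = n.

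| Subjects completing unaided | Proportion | Exact 90% CI |
|---|---|---|
| 50/50 | 100% | 94.2% to 100% |
| 45/50 | 90% | 80.1% to 96.0% |
| 40/50 | 80% | 68.4% to 88.7% |

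The subject is the safer unit because a patient's two incisions are likely to be alike. Per incision, at an assumed 90% unaided, the half-width 1.645 × √(0.9 × 0.1 / n_eff), with n_eff = 100/(1 + ICC), is 4.9 percentage points for ICC = 0 (n_eff = 100) and 7.0 points for ICC = 1 (n_eff = 50). Either way, the planned sample gives a usable estimate; what is missing is the data item and the objective.

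**The case against.** The strongest reply is that self-use is already built into the design. The patient is the prescribed operator, so an incision made by staff would depart from the Protocol. Section 16.3 has the primary analysis re-assessed if more than 10% of patients (more than 5 of 50) have major violations, and Section 24.2 provides for checking adherence. The coordinator's stated tasks do not include assisting. The statement in Section 21 that "risks have been minimized through selection of the Investigator who is experienced in capillary blood sampling" concerns risk and does not suggest hands-on help. All of this stands. It leaves verbal prompting and minor correction, which would not clearly count as deviations.

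A second reply is that the CRF is not shown and may hold such a field. Table 1 is only an overview, and the flow chart shows that more is collected. That also stands, so the point is limited to listed items. Even if a field exists, no objective uses it.

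Third, a failed firing would probably show as little or no blood. That is partly true, but a low volume does not separate poor yield from a user error, and a corrected second attempt could conceal either.

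A reader might infer that the trial cannot answer its question at all, or that any amount of staff help could pass unnoticed. The documents do not support this. Volume, pain and adverse events from patient-performed sampling bear on lay use, and the Study Summary, Section 14 and the synopsis frame the study as safety and performance. A reader might also want helped draws scored as volume failures. That would mix device yield with operator independence, whereas objective 1 asks only whether the volume can be collected.

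**Conclusion.** The point holds in a limited form. The planned endpoints are sound for what they measure and give indirect evidence on lay use. The no-intervention element of Section 13 has no objective and no listed data item, and permitted help is undefined, so that element cannot be shown. This is a gap between aim and measurement, not an error in any figure, and an SAP cannot close it after the event.

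Its numerical size is unknown. The helped-incision counts above are assumptions with no basis in the Protocol and show only what the data could fail to distinguish. The conclusion assumes that the CRF holds no assistance field beyond the items listed. Since 50 subjects suffice for the measure, this is a cheap improvement and no reason to redesign the trial.

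**What to change.** - **Table 1, per incision:** add (a) help from study staff during the incision or collection: none, verbal or physical, and whether the helper was medically qualified; and (b) device activated at first attempt: yes or no. The qualification item matters because Section 13 refers to medically qualified practitioners and the coordinator is not described as one. The explanation given beforehand is not counted as help.
- **Section 15.5 or 15.6:** state what help staff may give once the patient has begun.
- **Section 14.2:** add the proportion of subjects who completed their incisions unaided, with an exact 90% CI on n = 50.
- **Section 14.1:** leave the volume objective unchanged. Report separately, as a supportive lay-use result, either volume success among unaided incisions or the share of all incisions both unaided and adequate. The second keeps every incision in the denominator.

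The cost is two CRF fields, which the coordinator already on site can complete, and one objective line; no extra subjects are needed. The downside is that the lay-use result may look less favourable than volume alone.

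If the sponsor does not want this, narrow the aim in Section 13 and the Study Summary to volume, pain and safety of patient-performed sampling at a supervised site.
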